- Laboratory screening orders (CBC, chemistry panel, pregnancy test, HIV status)
- Patients will be prescribed topical corticosteroid (prednisolone acetate 1%) to be used one drop in affected eye four times per day (this is typical standard of care)
- Patients requiring management of elevated IOP will be prescribed IOP-lowering medication according to treating ophthalmologist's discretion and best medical judgment

Exam 1 Randomization and Procedures

[figure not shown]
- Review of results of in- house CMV PCR and laboratory results
- Consent, enrollment, randomization to treatment arm if participants meet eligibility criteria
- Clinical eye examination (in the following order: visual acuity, slit lamp examination of anterior segment, intraocular pressure assessment, confocal microscopy)

Randomization to 1 of 3 arms

Exam 2 (Day 7) Follow-up

- Clinical eye examination (in the following order: visual acuity, slit lamp examination of anterior segment, intraocular pressure assessment)
- **Anterior chamber paracentesis #2**
- **Assessment of clinical quiescence (grading anterior chamber cell)**
- Laboratory monitoring orders (complete blood count, complete metabolic panel)

Exam 3 (Day 21) Final visit for trial I

Trial II

**Exam 1
(Re-randomization)**

Clinically inactive (< 1+ anterior chamber cell)
for at least 2 weeks with at least 2 weeks
wash-out period (no antivirals)

- Clinical eye examination (in the following order, VA, slit lamp examination of anterior segment, IOP)
- **Suppressive treatment initiation (randomized to 1 of 3 arms)**

Group 1: Oral
valganciclovir N=35

Group 2: Topical
ganciclovir 2% N=35

Group 3: Placebo
N=35

**Exam 2
(1 month after
randomization)**

- Clinical eye examination (in following order, VA, slit lamp examination of anterior segment, IOP)
- **Assessment for recurrence of inflammation**
- **Anterior chamber paracentesis #3 if recurrent inflammation (participant exits study if recurrent inflammation)**

**Exam 3
(3 months after
randomization)**

- Clinical eye examination (in following order, VA, slit lamp examination of anterior segment, IOP)
- **Assessment for recurrence of inflammation**
- Confocal or specular microscopy if recurrent
- **Anterior chamber paracentesis #3 if recurrent inflammation (participant exits study if recurrent inflammation)**

**Exam 4
(5 months after
randomization)**

- Clinical eye examination (in following order, VA, slit lamp examination of anterior segment, IOP)

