- **Assessment for recurrence of inflammation**
- Confocal or specular microscopy if recurrent
- **Anterior chamber paracentesis #3 if recurrent inflammation (participant exits study if recurrent inflammation)**

**Exam 5
(7 months after
randomization)**

- Clinical eye examination (in following order, VA, slit lamp examination of anterior segment, IOP)
- **Assessment for recurrence of inflammation**
- Confocal or specular microscopy if recurrent
- **Anterior chamber paracentesis #3 if recurrent inflammation (participant exits study if recurrent inflammation)**

**Exam 6
(9 months after
randomization)**

- Clinical eye examination (in following order, VA, slit lamp examination of anterior segment, IOP)
- **Assessment for recurrence of inflammation**
- Confocal or specular microscopy if recurrent
- **Anterior chamber paracentesis #3 if recurrent inflammation (participant exits study if recurrent inflammation)**

**Exam 7
(11 months after
randomization)**

- Clinical eye examination (in following order, VA, slit lamp examination of anterior segment, IOP)
- **Assessment for recurrence of inflammation**
- **Anterior chamber paracentesis #3 if recurrent inflammation (participant exits study if recurrent inflammation)**

Exam 8
(12 months after
randomization,
Final Visit)

- Clinical eye examination (in the following order, VA, slit lamp examination of anterior segment, IOP)
- **Assessment for recurrence of inflammation**
- **Anterior chamber paracentesis #3 if recurrent inflammation (participant exits study if recurrent inflammation)**

Note that participants will be advised to contact their local site clinical coordinator or study ophthalmologist if they are having symptoms of recurrent inflammation. Recurrent inflammation is typically symptomatic (characterized by ocular redness, decreased vision, light sensitivity, and pain). Thus, participants will be evaluated for symptoms of recurrent inflammation, which may occur between study visits, during which they would have clinical eye examination, anterior chamber paracentesis #3 (if there is recurrent (active) inflammation).

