4.3 End of Study Definition

A participant is considered to have completed the study if he or she has completed all visits and procedures and exams of the study described in Assessments and Procedures **Section 7.1**.

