### **3.7. Timing of outcome assessments**

In Trial I, outcome assessments will be conducted each week since beginning of treatment, with a window of 5 to 9 days for the final outcome. In Trial II, outcome assessments will be conducted every 3 months since beginning of treatment, with a window of 5 to 7 months for the final outcome.

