## 4.2. Protocol deviations

The primary analyses will be conducted on an intent-to-treat basis. Individuals who receive the mandated dose of the medication to which they have been randomized are assumed adherent.

Adherence will be assessed via a study calendar patients use to report adherence and objectively by pill counting and weighing of medication bottles. The details of the assessments are included in the Protocol. Participants who miss a scheduled dose of medication will be instructed to continue with their next scheduled dose of tablets or eye drops.

In the event an individual receives a medication to which they were not randomized, a protocol deviation will be reported. A per protocol analysis will be conducted using only individuals who were adherent (an analysis to be sharply distinguished from the primary intent-to-treat analysis).

Any individual who receives even one dose of study medication or placebo is included in the safety analysis population. Any individual who receives study medication and who has a follow-up visit during the prescribed period is included in the complete case analysis.

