## 6. Analysis

### 6.1. Outcome definitions

Trial I: Primary Endpoint: Log-transformed viral load after 7 days of treatment

Secondary Endpoints:

- Anterior chamber cell (days 7, 21)
- Intraocular pressure (days 7, 21)
- Visual acuity (days 7, 21)
- Controlled inactivity defined as  $\leq 0.5+$  anterior chamber cell AND intraocular pressure  $< 24$  mmHg AND no cornea edema AND no active KPs (day 7, 21).

Trial II: Primary Endpoint: Proportion recurrent inflammation ( $\geq 1+$  anterior chamber cell at any study visit) over 12 months

Secondary Endpoints:

- Prevalence of CMV associated with recurrence of uveitis

1a. The Aim 1 primary outcome **viral load after 7 days of treatment** will use the results from quantitative PCR at 7 days of treatment or placebo therapy (day 7 of trial). All quantitative PCR viral loads will undergo base-10 logarithm-transformation, with units converting from IU/mL to log IU/mL. Log-transformed viral loads will be used because the range of viral loads can be wide and dealing with very large and very small numbers is handled more efficiently using a logarithmic scale. Such normalization of the distribution of viral loads is consistent with standard practice in viral load analyses.

1b. **Clinical outcomes and inactivity:** At each study visit participants will be clinically examined for ocular outcomes including AC inflammatory cells, intraocular pressure, and visual acuity. A study ophthalmologist will make a clinical determination as to whether the patient's inflammation is considered inactive. Clinical outcomes and the proportion of participants that

achieve quiescence by day 7 and 21 will be compared by arm. Patients will also be administered a questionnaire querying when they felt symptomatic improvement in their condition. This analysis will be viewed as hypothesis generating and will be treated as supplementary and in addition to the main finding.

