### Primary Analysis Trial II

**Aim 2a. Recurrence rate of anterior uveitis over 12 months:** The proposed analysis for sub-Aim 2a (Trial II), which is a clinical outcome, is a log-binomial regression model to compare cumulative inflammatory recurrence (based on anterior chamber cell  $\geq 1+$  cell) between treatment groups. We will censor participants at the first recurrence of anterior uveitis (based on anterior chamber cell  $\geq 1+$  cell) or 12 months. The model includes indicators for the treatment arm and indicators for each site used to stratify the randomization. We will estimate the risk ratios from the model for the two primary comparisons, *oral valganciclovir* vs. *topical ganciclovir 2%*, and *oral valganciclovir* vs. *placebo*. We will use a simulation-based permutation test to estimate p-values, and will report max-T simultaneous confidence intervals and p-values adjusted for the two pair-wise comparisons (*oral valganciclovir* vs. *topical ganciclovir 2%*, *oral valganciclovir* vs. *placebo*). Pre-specified sub-group analyses by sex will be performed.

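### SAP 4.2 defines complete cases by attendance, which does not fit Trial II because recurrence ends attendance; the plan should state whose outcome counts as observed and how non-recurrent dropouts are handled

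*SAP*

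**What the plan says.** - **Analysis set.** SAP 4.2 has one sentence for both trials: "Any individual who receives study medication and who has a follow-up visit during the prescribed period is included in the complete case analysis". It does not say what the period is.
- **Exit.** The Trial II schema (Protocol 1.1) notes at every exam from month 1 to month 12 "participant exits study if recurrent inflammation". Recurrences may also be seen outside the schedule: "participants will be evaluated for symptoms of recurrent inflammation, which may occur between study visits".
- **Window.** SAP 3.7 gives the Trial II outcome assessment "with a window of 5 to 7 months for the final outcome". SAP 3.6 times the final Trial II analysis at 7 months after the last enrollee's treatment, and the objectives table in Protocol section 3 still gives a 6-month endpoint.
- **Endpoint and model.** SAP 6.1 defines recurrence by "anterior chamber cell at any study visit) over 12 months". SAP 6.2 fits a log-binomial model for cumulative recurrence with terms for arm and site only. It adds "We will censor participants at the first recurrence of anterior uveitis" or at 12 months. Loss to follow-up is not mentioned there.
- **Completion.** Protocol 4.3 counts a participant as having completed the study "if he or she has completed all visits and procedures and exams of the study".
- **Missing data.** SAP 6.3 uses complete cases when at most 10% of outcomes are missing. Above that it adds inverse probability weighting of complete cases as a sensitivity analysis. SAP 3.3 plans for 20% loss in Trial II.

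**The concern.** An attendance rule works for Trial I, where the outcome is measured at one visit around day 7. In Trial II the primary event itself stops attendance, so whether someone has a visit in a late period depends on whether and when they recurred.

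Two readings of the undefined period cause trouble. If it is the written 5-to-7-month window, early recurrers leave the analysis set, and proportionally more of them leave from the arm with more recurrences. If it is the full 12 months, one visit at month 1 is enough to qualify. A participant then lost without recurrence enters a binary model with no time axis, and the only code on offer is no recurrence.

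The primary risks and risk ratios would then depend on a phrase that could be interpreted after unmasking.

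**Working it through.** **Inputs.** 12-month risks of 25% (placebo) and 65% (oral valganciclovir), 28 per arm after 20% loss, two-sided alpha 0.025 and a two-sample z-test (SAP 3.3); 35 randomised per arm (Protocol 1.1). The documents give no timing for recurrence or loss. Constant hazards and recurrences examined at onset are my assumptions.

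**1. The plan's own figure.** 105 × 0.8 / 3 = 28 per arm. The pooled proportion is 0.45. The standard error under the null is √(2 × 0.45 × 0.55 / 28) = 0.133, and under the alternative √((0.1875 + 0.2275) / 28) = 0.122. Power = Φ((0.40 − 2.241 × 0.133) / 0.122) ≈ 0.80. The stated 80% is reproduced.

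**2. Recurrences before month 5, ignoring loss.** The share is (1 − (1 − p)^(5/12)) / p.
- Placebo: 0.113 / 0.25 = 45%.
- Oral: 0.354 / 0.65 = 55%.

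Among those still in at month 5, the risk to month 12 is 1 − (1 − p)^(7/12), which is 15.4% and 45.8%.

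**3. Adding 20% loss per arm, spread over the year.** Let L = −ln(1 − p), D = −ln(0.8) = 0.223, s = L/(L + D), and E(w) = exp(−(L + D)w/12), the share neither recurred nor lost by month w.
- Placebo: L = 0.288, s = 0.563, E(5) = 0.808, E(12) = 0.600.
- Oral: L = 1.050, s = 0.825, E(5) = 0.588, E(12) = 0.280.

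The share with an observed recurrence is R = s(1 − E(12)): 0.563 × 0.400 = 0.225 and 0.825 × 0.720 = 0.594.

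*Visit required in months 5 to 7.* Risk = s(E(5) − E(12))/E(5).
- Placebo: 0.563 × 0.208 / 0.808 = 14.5%.
- Oral: 0.825 × 0.308 / 0.588 = 43.2%.

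The share of observed recurrences left out is s(1 − E(5))/R, or 48% and 57%.

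*Any follow-up visit in 12 months, dropouts coded as no recurrence.* About 98.2% of each arm has a month-1 visit or an earlier recurrence. Risk = R/0.982: 22.9% and 60.5%.

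*Recurrence at any time, or month 12 reached without recurrence; all others dropped.* Risk = R/(R + E(12)).
- Placebo: 0.225 / 0.825 = 27.3%.
- Oral: 0.594 / 0.874 = 68.0%.

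| Rule | Placebo | Oral | Difference (points) | Risk ratio | Power |
|---|---|---|---|---|---|
| Assumed truth | 25% | 65% | 40 | 2.60 | 80% (plan) |
| Visit in months 5 to 7 | 14.5% | 43.2% | 28.7 | 2.98 | about 51% |
| Any visit, dropouts as no recurrence | 22.9% | 60.5% | 37.5 | 2.63 | about 84% |
| Outcome known, others dropped | 27.3% | 68.0% | 40.7 | 2.49 | about 84% |

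Power in the last three rows comes from simulation with 35 randomised per arm and a pooled z-test at 0.025. The simulated risks agree with the formulas to within about 0.1 point.

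**4. Other assumptions.** The simulation also varied the Weibull shape from 0.7 to 1.5 and loss (placebo/oral) over 20/20, 10/30 and 30/10 percent.
- The months-5-to-7 rule leaves out 31% to 71% of recurrences.
- The difference is 32 to 41 points when dropouts count as recurrence-free, and 37 to 44 when they are dropped.

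At constant hazard with unequal loss, risk ratios are:
- Dropouts as recurrence-free: 0.580/0.240 = 2.42 (loss 10/30) and 0.628/0.218 = 2.88 (loss 30/10).
- Dropouts removed: 0.697/0.261 = 2.67 and 0.664/0.288 = 2.31.

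Both sets miss the true 2.60 by similar amounts.

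**The case against.** The documents contain a better reading than either of the two above. SAP 6.1 counts recurrence at any study visit. SAP 6.3 turns on missing outcome data, not on attendance. Protocol 8.3.1 treats loss to follow-up and dropout as missing data and promises sensitivity analyses that assign outcomes. Protocol 6.1 keeps withdrawn participants in the primary analysis. SAP Table 1 draws recurrences from within the completers (60% of 18 ≈ 11; 60% of 38 ≈ 23), and the sample size removes lost participants from the denominator. A recurrence visit is itself a follow-up visit, SAP 4.2 says who is included without saying only those, and no analysis set cites Protocol 4.3. All of this stands, and it rules out three stronger conclusions that a reader might draw.

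- *Every reading gives a wrong primary result.* Not so. The third reading loses no recurrence and codes no dropout as recurrence-free.
- *Most recurrences are lost.* Under the written window it is about half. The 93% and 95% figures need a window opening at month 11, which no section states.
- *Counting dropouts as recurrence-free cuts power to 72%.* That takes 0.8 × 25% = 20% against 0.8 × 65% = 52% at 35 per arm, as if all loss came before any recurrence. With equal loss spread over the year, power is about 84%, so there is no deficit.

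What the objection leaves open is that SAP 4.2 does not state the third reading. That reading also overstates risk if non-recurrent dropouts are simply removed, since early recurrers had less time to be lost. The weighting in SAP 6.3 reweights complete cases and is only a sensitivity analysis. In the illustration, loss is unrelated to baseline, so baseline weights would leave the 27% and 68% unchanged.

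**Conclusion.** The point holds as a gap in the definition of the Trial II primary analysis set. Read literally with the SAP's own window, the rule discards roughly half of the primary events. It shrinks the risk difference from 40 to about 29 points while raising the risk ratio from 2.60 to about 2.98. Read as 12 months, it does little harm when loss is equal, but it biases the comparison when loss differs by arm.

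The sections on endpoint and missing data point to a sounder rule, so this is a wording conflict with a clear resolution and not a proven error in the eventual analysis. The sizes rest on SAP 3.3's risks, the planned 20% loss and assumed timing. The mechanism does not depend on the timing: recurrence ends attendance, the period is undefined, and the model has no stated place for a non-recurrent dropout.

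**What to change.** 1. For Trial II, replace the SAP 4.2 sentence. Anterior chamber cell of 1+ or more at any scheduled or unscheduled visit through month 12 is an observed recurrence, whatever its date. No recurrence requires the month-12 exam within its window, and that window must be stated.
2. State that participants lost before month 12 without recurrence are censored or missing. Name the method by which they enter the primary 12-month risk comparison: Kaplan-Meier risk, risk weighted by the inverse probability of remaining uncensored over time, or multiple imputation. Item 1 without this replaces one bias with another. SAP 6.2 already refers to imputation in SAP 6.3, but that section describes only weighting.
3. Reconcile the 5-to-7-month window (SAP 3.7) and the 7-month analysis timing (SAP 3.6) with the 12-month endpoint.
4. Word Protocol 4.3 so that leaving at recurrence, with its visit done, counts as completing Trial II.

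The cost is SAP wording, one protocol sentence and slightly more analysis work. More participants will be classed as missing than if any single visit sufficed, so the 10% missing-data threshold will be crossed more readily. The change should be made before Trial II outcomes are unmasked.

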6 PARTICIPANT DISCONTINUATION/WITHDRAWAL

6.1 Participant Discontinuation/Withdrawal from the Study

Participants are free to withdraw from participation in the study at any time upon request. The reason for participant discontinuation or withdrawal from the study will be recorded on the final form. Subjects who sign the informed consent form and are randomized but do not receive the study intervention may not be replaced and will be included in the intent to treat analysis. Subjects who sign the informed consent form, and are randomized and receive the study intervention, and subsequently withdraw, or are withdrawn or discontinued from the study, will not be replaced and will be included in the primary analysis.

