Futility. Early discontinuation due to the unlikelihood of significant findings conditional on interim results may be considered, based on the original sample size considerations. For evaluating futility, we propose to use a simulation-based approach²⁴ that estimates conditional power under the assumed design effect for the remainder of participants and under the current trend observed at the interim analysis. We propose that the DSMC consider discontinuation for futility if the conditional power to detect a difference in viral load in Trial I and recurrence in trial II drops below 20% at the interim analysis under the assumed design effect for the remainder of participants yet to be enrolled.

Population for Analyses

Individual level missing data (due to loss to follow-up or dropouts) is expected. Complete analysis will be reported. Missing values will be tabulated by treatment arm, and study site. Sensitivity analysis assigning outcomes to the missing values will be reported. Additionally, analyses will be reported in which we adjust for any baseline covariate known to be a predictor of missing outcome data. **Please refer to the SAP for further details regarding analyses.**

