### 3.4. Statistical framework

For each trial, we propose two primary analyses:

- Comparison of oral valganciclovir and placebo arms (superiority comparison)
- Comparison of oral valganciclovir and topical ganciclovir 2% arms (superiority comparison)

Analyses of the trials will be intention to treat, with participants analyzed as they are randomized. We plan to use a frequentist approach to the analysis, with appropriate control for multiple testing and any interim analyses (details below).

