## 6.2. Analysis methods

Patients will be analyzed according to their assigned treatment (intention-to-treat).

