## 6.3. Missing data handling

In Trial I and Trial II, we will report the fraction missing or lost to follow-up by study arm. If  $\leq 10\%$  of enrolled participants are missing outcome data, complete case analyses will be conducted. If  $> 10\%$  of enrolled participants are missing outcome data, inverse probability weighting will be used to weight complete cases by the inverse of an estimate of the probability of an outcome being observed as a sensitivity analysis. Weights will be constructed with baseline characteristics likely to predict missingness that are also associated with the outcome, including primary variables (viral load measurements, time to recurrence, treatment assignment, site) and auxiliary variables (baseline characteristics, partial outcome data, adherence measures, prior treatment history).

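### SAP 4.2 makes taking study medication a condition of the complete-case set, so a never-treated participant with an observed outcome can be left out of an analysis the Protocol says includes them

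*SAP*

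**What the plan says.** On the principle the documents agree. SAP 3.4 states: "Analyses of the trials will be intention to treat, with participants analyzed as they are randomized". SAP 4.2 opens with "The primary analyses will be conducted on an intent-to-treat basis", and SAP 6.2 repeats that the assigned treatment governs. Protocol 6.1 covers the untreated case directly: consenting participants who are "randomized but do not receive the study intervention may not be replaced and will be included in the intent to treat analysis".

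The analysis sets are then described at the end of SAP 4.2. For safety: "Any individual who receives even one dose of study medication or placebo is included in the safety analysis population". For efficacy, in the next sentence: "Any individual who receives study medication and who has a follow-up visit during the prescribed period is included in the complete case analysis". No other passage says who belongs to the complete-case set.

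SAP 6.3 says when that set is used. If no more than 10% "of enrolled participants are missing outcome data, complete case analyses will be conducted". Above 10%, complete cases are reweighted by the inverse probability of being observed, as a sensitivity analysis. The Protocol's paragraph on analysis populations, at the end of section 8.3.1, says only "Complete analysis will be reported" and attaches no condition on treatment.

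**The concern.** Whether a participant takes the first dose is settled after randomisation. Selecting on it removes the protection that randomisation gives, which is why Protocol 6.1 keeps untreated participants in. The SAP sentence reintroduces that selection in the set from which the main result will be computed. An analyst who follows SAP 4.2 and one who follows Protocol 6.1 would build different datasets whenever a never-starter has a day-7 viral load in Trial I or a known recurrence status in Trial II. At stake is which effect is reported under the intention-to-treat label, and whether that choice is fixed before the data are seen.

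**Working it through.** **1. Who is treated differently.** Set the two rules side by side for the four kinds of randomised participant.

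| Participant | Protocol 6.1 with SAP 3.4 | SAP 4.2 complete-case sentence |
|---|---|---|
| Started, outcome observed | in | in |
| Started, no outcome | in principle in, but nothing to analyse | out |
| Never started, no outcome | in principle in, but nothing to analyse | out |
| Never started, outcome observed | in | out |

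The second and third rows are ordinary missing data and are not at issue. The conflict is confined to the fourth row.

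**2. Whether another rule brings the fourth row back.** Both branches of SAP 6.3 work from complete cases, so the weighted analysis inherits the same set. The Protocol's sensitivity analysis assigns values to missing outcomes, but a fourth-row outcome is not missing. SAP 3.7 counts assessment times from the start of treatment, a date that a never-starter does not have. None of these settles the matter.

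**3. Scale, from the plan's own Trial I figures (SAP 3.3).** Residual SD = 0.98 × √(1 − 0.74²) = 0.659, given as 0.66. The design effect is 3.11 − 2.61 = 0.50 log10. With 35 per arm the standard error of the difference is 0.66 × √(2/35) = 0.158. The two-sample t-test at two-sided alpha 0.025 gives 80.8% power, which reproduces the stated 80%. Enrolment is 105/0.90 = 116.7, so 117. (Protocol 8.2 prints a different correlation. That is a separate matter and enters here only through the standard error, used as a yardstick.)

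**4. Size if never-starters are equally common in all arms.** The documents give no non-initiation rate, so let f be the assumed share of each arm's observed outcomes that come from never-starters, and suppose they have no drug effect. Then

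- effect in starters = 0.50
- effect by assignment = 0.50 × (1 − f)

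| f (assumed) | Trial I, by assignment | Gap from 0.50 | Trial II, by assignment (SAP design difference 40 points) |
|---|---|---|---|
| 0 | 0.500 | 0 | 40.0 |
| 1% | 0.495 | 0.005 | 39.6 |
| 2% | 0.490 | 0.010 | 39.2 |
| 5% | 0.475 | 0.025 | 38.0 |
| 10% | 0.450 | 0.050 | 36.0 |

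One never-starter in an arm of 35 is f = 1/35 = 2.9%; f = 5% is 0.05 × 35 = 1.75 people. The gap at 5% is 0.025/0.158 = 0.16 standard errors, and at 10% it is 0.050/0.158 = 0.32.

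**5. Size if only the active arm is affected.** Let s be the amount by which never-starters' untreated day-7 viral load differs from that of other participants. By randomisation the comparator arm contains the same kind of people, and there they all start.

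- comparator mean = 3.11 + f·s
- active mean, everyone = (1 − f) × 2.61 + f × (3.11 + s), so the effect by assignment = 0.50 × (1 − f)
- active mean, starters only = 2.61, so the effect under the SAP 4.2 rule = 0.50 + f·s

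At f = 5% the effect by assignment is 0.475. The SAP 4.2 rule gives 0.450, 0.475, 0.500, 0.525 or 0.550 for s = −1, −0.5, 0, +0.5 or +1 log10. The gap is f × (s + 0.50), so it is negative when s is below −0.50 and positive when s is above it.

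**The case against.** The case for leaving the text alone is that the SAP declares intention to treat three times. The sentence says who is included and never says that only they are. The per-protocol sentence just before these set definitions does use a restrictive word, so the authors know how to exclude. SAP 6.3 also speaks of missing outcomes, not missed doses, which suggests that completeness means an observed outcome.

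Part of this stands: exclusion is not stated outright and was probably not intended. It does not remove the conflict. The safety sentence immediately before has the same form and is plainly a membership rule, since nobody would place a never-dosed person in the safety set; the next sentence reads the same way. The statements in SAP 3.4 and 6.2 fix the arm in which a participant is counted, but they do not cancel a dose condition placed on the dataset.

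A second objection stands in full: the affected group is narrow. Treatment starts at the randomisation visit in the Protocol's schedule of activities, and a Trial I never-starter must still undergo the day-7 paracentesis to have an outcome. The SAP revision history mentions full adherence to assigned treatment. It does not say which trial it describes, but it lends no support to a high rate of non-initiation.

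A reader might also infer that placebo recipients are excluded, because the safety sentence names placebo and the complete-case sentence does not. The documents do not support that. Placebo is one arm of a primary comparison, and the Protocol uses the term study medication for the masked products generally. It is a slip in wording.

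**Conclusion.** The inconsistency is real. For a never-starter with an observed primary outcome, SAP 4.2 and Protocol 6.1 give opposite answers, and SAP 6.3 carries the SAP 4.2 rule into the reported analysis. The number affected is not given, is probably small and may be zero; at zero the two sets are identical. Every non-initiation rate and prognostic shift used above is an assumption, and so is the absence of any drug effect in never-starters.

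A reader might go further and infer that the reported intention-to-treat effect is in fact an effect in treated participants, and an overstated one. The documents do not support that. Nothing shows that any outcome will be dropped. With equal non-initiation, the starters' effect answers a different question and is modestly larger. With unequal non-initiation it can be smaller than, equal to or larger than the effect of assignment. The double-masked design, with tablets and drops in every arm, gives no evident reason to expect one-sided non-initiation.

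Nor should any loss of power be charged to this sentence. Dilution by never-starters belongs to the analysis as randomised, and it would be present after the correction as well.

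The point is therefore modest in size, but worth settling before the data are unmasked for analysis, because it decides who is in the primary dataset.

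**What to change.** Replace the complete-case sentence in SAP 4.2 with: *Every randomised participant with an observed primary outcome is included in the complete-case analysis in the arm assigned, whether or not any study medication or placebo was taken.* Keep dose receipt as a condition only for the safety set and for any separately named per-protocol set. The new sentence also removes the placebo slip. State in SAP 3.7 the date from which the outcome window runs for someone who never starts, since the present text offers none.

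The cost is one replaced sentence and one clarification, with no change to data collection or sample size. The only statistical price is slight dilution of the estimate if some participants never start, which the commitment to analyse as randomised already accepts.
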